6.1.1. Analysis Populations

Patient populations are defined in [Table AMAH.6.1](#) along with the analysis they will be used to conduct. Patients will be analyzed according to the treatment to which they were assigned for all populations.

Table AMAH.6.1. Definition of Population

Population	Description
All Entered Patients	All patients who have signed the informed consent.
Intent-to-Treat (ITT) Population	All enrolled patients defined as those who have signed the informed consent and have been assigned to treatment in interactive web-response system (IWRS). Patients will be analyzed according to the treatment to which they were assigned. All efficacy and safety analyses will use ITT population.

Patients will be grouped based on the following 3 patient cohorts:

- (1) Patients assigned to 250 mg mirikizumab Q8W SC in Study AMAH, excluding patients who received secukinumab during the qualifying period of their originating study.
- (2) Patients assigned to 125 mg mirikizumab Q8W SC in Study AMAH.

(3) Patients assigned to 250 mg mirikizumab Q8W SC in Study AMAH who received secukinumab during the qualifying period of their originating study.

All efficacy analyses, including health outcome endpoints, will be conducted separately in patients of cohort (1), (2), and (3) on the ITT population. All safety analyses will be conducted on ITT population by cohort.

6.1.2. Baseline Definition

Unless otherwise specified, all references to baseline for efficacy and health outcomes related endpoints in this study protocol refer to baseline values of the originating study (that is, the study in which the patient received their first dose for this program).

6.1.3. Analysis Methods

For assessments of the primary endpoints and other binary efficacy and health outcomes, proportions for each cohort along with the 95% 2-sided asymptotic (i.e., not continuity corrected) confidence intervals (CIs) will be provided. Modified Non-responder Imputation (mNRI) method will be used to estimate the percentage of patients achieving response across post-baseline visits (see Section 6.3.4). In addition, multiple imputation (MI), Non-responder Imputation (NRI), and as Observed methods will be used as secondary analysis (see Section 6.3.1, Section 6.3.2, Section 6.3.1).

For continuous efficacy and health outcomes, MI method will be used for summaries.

Summaries based on observed data at each post-baseline visit will be provided (see Section 6.3.1).

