10.3. Statistical Analyses

10.3.1. General Statistical Considerations

Statistical analysis of this study will be the responsibility of Lilly or its designee.

Any change to the data analysis methods described in the protocol will require an amendment ONLY if it changes a principal feature of the protocol. Any other change to the data analysis methods described in the protocol, and the justification for making the change, will be described in the clinical study report. Additional exploratory analyses of the data will be conducted as deemed appropriate.

For all safety, efficacy and health outcomes analysis, the ITT population will be used unless otherwise stated.

Continuous data will be summarized in terms of the mean, standard deviation, minimum, maximum, median, and number of observations. Categorical data will be summarized as frequency counts and percentages. The analysis will be focused on point estimates and confidence intervals. Thus, no hypothesis testing will be performed, and control for multiplicity is not applicable. Efficacy and safety summaries will be provided by the following 3 cohorts:

- (1) Patients assigned to 250 mg mirikizumab Q8W SC in Study AMAH, excluding patients who received secukinumab during the qualifying period of their originating study.
- (2) Patients assigned to 125 mg mirikizumab Q8W SC in Study AMAH
- (3) Patients who received secukinumab during the qualifying period of their originating study.

Additional cohorts for further analysis may be defined in the SAP and summarized. Sensitivity analyses may be done by excluding from Cohort (1) patients who were receiving placebo during the qualifying period of their originator study.

Unless otherwise specified, all references to baseline for efficacy and health outcomes related endpoints in this study protocol refer to baseline values of the originating study. Detailed definitions of baseline for safety, vital sign, laboratory, and immunogenicity related analyses will be described in the SAP prior to first unblinded analysis.

For assessment of categorical efficacy endpoints, proportions and 95% confidence intervals will be reported using the simple asymptotic method, without continuity correction (that is, normal approximation to the binomial distribution).

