5.2. Determination of Sample Size

The sample size for Study AMAH will be determined by the number of patients who enroll in Study AMAH from the originator studies. Approximate planned sample sizes for Studies AMAF, AMAJ, AMAK, and AMBK are respectively 205, 1440, 500, and 300. Based on the assumption that 80% to 90% of patients complete the originator studies and 80% to 90% of the completers continue on into Study AMAH, Lilly anticipates that approximately 1600 to 2000 patients will enter Study AMAH.

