6.4. Multiple Comparisons/Multiplicity

The analysis will be focused on point estimates and confidence intervals. Thus, no hypothesis testing will be performed, and adjustments due to multiple testing is not to be accounted for.

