sPGA	sPGA (0,1) (Primary)	Descriptive analysis with Observed, NRI, mNRI and Multiple Imputation	ITT - patients who entered Study AMAH with sPGA (0,1)	All visits in corresponding periods
	sPGA (0); sPGA (0,1) (Secondary)	Descriptive analysis with Observed, NRI, mNRI and Multiple Imputation	ITT	All visits in corresponding periods
PSS	PSS symptoms score of 0;	Descriptive analysis with Observed, NRI, mNRI and Multiple Imputation	ITT – patients with a PSS symptoms score ≥ 1 at Baseline	All visits in corresponding periods
	PSS signs score of 0;	Descriptive analysis with Observed, NRI, mNRI and Multiple Imputation	ITT – patients with a PSS signs score ≥ 1 at Baseline	All visits in corresponding periods
PSSI	PSSI change from baseline	Descriptive analysis with Observed and Multiple Imputation	ITT - patients with Scalp Involvement at Baseline	All visits in corresponding periods
	PSSI = 0	Descriptive analysis with Observed, NRI, mNRI and Multiple Imputation	ITT – patients with Scalp Involvement at Baseline	All visits in corresponding periods
PPASI	PPASI change from baseline	Descriptive analysis with Observed and Multiple Imputation	ITT - patients with Palmoplantar Involvement at Baseline	All visits in corresponding periods

Measure	Variable	Analysis Method (Section 6.1.3)	Population (Section 6.1.1)	Time Point
	PPASI 50; PPASI 75; PPASI 100	Descriptive analysis with Observed, NRI, mNRI and Multiple Imputation	ITT – patients with Palmoplantar Involvement at Baseline	All visits in corresponding periods
NAPSI	NAPSI change from baseline	Descriptive analysis with Observed and Multiple Imputation	ITT - patients with Nail Psoriasis Involvement at Baseline	All visits in corresponding periods
	NAPSI = 0	Descriptive analysis with Observed, NRI, mNRI and Multiple Imputation	ITT – patients with Nail Psoriasis Involvement at Baseline	All visits in corresponding periods
DLQI	DLQI (0,1)	Descriptive analysis with Observed, NRI, mNRI and Multiple Imputation	ITT - patients with Baseline DLQI > 1	All visits in corresponding periods
	DLQI (0,1) and ≥5-point reduction from Baseline	Descriptive analysis with Observed, NRI, mNRI and Multiple Imputation	ITT – patients with DLQI ≥5 at Baseline	All visits in corresponding periods

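### Uncorrected Wald intervals are set for every binary endpoint with no alternative near 100% or in small denominators, where their coverage falls short of 95%

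*SAP*

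**What the plan says.** Protocol 10.3.1 states that for categorical efficacy endpoints "proportions and 95% confidence intervals will be reported using the simple asymptotic method, without continuity correction", which is the Wald interval. SAP 6.1.3 carries this over to the primary endpoints and all other binary efficacy and health outcomes: "95% 2-sided asymptotic (i.e., not continuity corrected) confidence intervals (CIs) will be provided", by cohort. Neither document names another interval for extreme proportions or small denominators, and SAP 6.9.5 plans no sensitivity analyses.

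SAP 6.4 explains why the interval carries weight: "The analysis will be focused on point estimates and confidence intervals", and no hypotheses are tested.

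SAP Table AMAH.6.4 restricts the two primary endpoints to patients who enter Study AMAH already in sPGA (0,1) or PASI 90 response, and reports them at all visits. The scalp, nail and palmoplantar endpoints are restricted by involvement, for example "ITT - patients with Nail Psoriasis Involvement at Baseline". Under SAP 6.1.1 every efficacy analysis is then done separately in three cohorts.

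On missing data, SAP 6.3.4 makes mNRI primary for binary outcomes. SAP 6.1.3 makes MI, NRI and as-observed secondary. SAP 6.3.2 pools imputed datasets by Rubin's rules.

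**The concern.** The Wald interval estimates the standard error from the observed proportion alone. As that proportion nears 1 the estimated error shrinks towards zero, so the interval is centred too high and is often too short. It can run past 100%, and it collapses to a point when every patient responds.

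The design makes high proportions plausible. A cohort defined by response at entry starts at 100% by construction, so early visits may lie close to that boundary. The as-observed analysis keeps only patients still on treatment at the visit, so dropouts do not pull the proportion down, while the denominator shrinks.

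At stake is the stated precision of durability. Someone who reads the lower limit as the rate at which response is at least maintained would be misled in the favourable direction.

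**Working it through.** **Inputs.** The method comes from protocol 10.3.1 and SAP 6.1.3. SAP 5.2 gives the only sizes: "Approximate planned sample sizes for Studies AMAF, AMAJ, AMAK, and AMBK are respectively 205, 1440, 500, and 300", with the assumption that "80% to 90% of patients complete the originator studies and 80% to 90% of the completers continue on into Study AMAH". No response rate, cohort size or subset size is stated, so n and p below are assumed and scanned.

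**The plan's own figure.** 205 + 1440 + 500 + 300 = 2445. Then 2445 × 0.80 × 0.80 = 1565 and 2445 × 0.90 × 0.90 = 1980. This agrees with SAP 5.2, which expects that "approximately 1600 to 2000 patients will enter Study AMAH". SAP section 5 notes that AMBK had not begun at SAP Version 2. Without its 300 patients, 2145 × 0.64 = 1373 and 2145 × 0.81 = 1737. The split over the three cohorts is not given.

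**Formulas**, with p̂ = x/n and z = 1.96:
- Wald: p̂ ± z√[p̂(1 − p̂)/n]
- Wilson: [p̂ + z²/2n ± z√(p̂(1 − p̂)/n + z²/4n²)] / (1 + z²/n)
- Exact coverage at true p: the sum of the binomial probabilities P(X = x) over all x whose interval contains p.

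**One case by hand, n=30, p=0.95.** The Wald interval contains 0.95 for x = 25 to 29. At x = 30 it is 100% to 100%, which misses, with probability 0.95³⁰ = 0.2146. For x ≤ 24 the upper limit is at most 94.3%, which misses, with probability 0.0033. Coverage = 1 − 0.2146 − 0.0033 = 78.2%.

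**Selected results (%)**

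| n | p | Wald coverage | Lower limit above p | Upper limit below p | Wilson coverage |
|---|---|---|---|---|---|
| 30 | 0.95 | 78.2 | 21.5 | 0.3 | 93.9 |
| 100 | 0.95 | 87.7 | 11.8 | 0.4 | 96.6 |
| 400 | 0.95 | 92.7 | 6.1 | 1.1 | 95.0 |
| 400 | 0.98 | 89.5 | 9.7 | 0.8 | 95.4 |
| 800 | 0.90 | 95.2 | 3.1 | 1.7 | 94.9 |
| 800 | 0.95 | 94.3 | 3.9 | 1.7 | 95.8 |

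The nominal miss is 2.5% on each side. At n=30 and p=0.98, Wald coverage falls to 45.4%.

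Over n = 300, 400, 500 and 800 with p = 0.90 to 0.95, Wald coverage is 92.6% to 95.2%, so the shortfall is at most 95 − 92.6 = 2.4 points. Coverage oscillates with n, and sizes in between can dip slightly lower (92.0% at n=323, p=0.95). For p = 0.70 to 0.85 and n of 50 or more it is 93.3% to 95.3%. Wilson is not exactly 95% either: over n = 30 to 700 at p = 0.90, 0.95 and 0.98 it ranges from 91.8% to 98.0%.

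**Limits at given counts**

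| Responders | Wald | Wilson |
|---|---|---|
| 30/30 | 100% to 100% | 88.6% to 100% |
| 29/30 | 90.2% to 103.1% | 83.3% to 99.4% |
| 380/400 | 92.9% to 97.1% | 92.4% to 96.7% |
| 760/800 | 93.5% to 96.5% | 93.3% to 96.3% |

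For 29/30, Wald is 0.9667 ± 1.96 × √(0.9667 × 0.0333/30) = 0.9667 ± 0.0642. For 30/30, the Wilson lower limit is n/(n + z²) = 30/33.84.

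**Scope.** These figures hold for a plain binomial proportion, that is, the observed and NRI analyses. MI and mNRI intervals add between-imputation variance, so their coverage also depends on the imputation. Their within-imputation variance is still p̂(1 − p̂)/n, which vanishes at 100%.

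**The case against.** The strongest reply is that the trial is not shown to be in the region where Wald fails, and much of it stands.

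- A reader might infer that the plan expects rates of 90% to 100%. It states no rate. Over 208 weeks, NRI counts all missing data as failure, and mNRI counts discontinuation for adverse events or lack of efficacy as failure. Both can pull later proportions into a range where Wald performs adequately.
- A reader might infer that the nail, scalp and palmoplantar analyses combine small denominators with proportions near 1. The documents do not show this. Those subsets are defined by involvement at originator baseline, not by response at entry, and their sizes are not given.
- A reader might infer that the primary intervals are materially wrong. With 1600 to 2000 patients in three cohorts, several hundred per cohort is a reasonable assumption. At 95% response, Wald and Wilson limits then differ by only 0.2 to 0.6 points for n = 300 to 800. The coverage table also does not describe the primary mNRI intervals.
- Nothing is decided by these intervals. There is no test, threshold or success criterion, SAP 6.2 calls the primary analysis descriptive, and the two documents agree on the method.

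What remains is that the interval has no fallback where it is known to fail, in a study whose output is estimates and intervals. The error also favours durability: at n=400 and p=0.95 the lower limit lies above the true rate 6.1% of the time, more than twice the nominal 2.5%.

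**Conclusion.** The concern holds in a limited form. Both documents specify the Wald interval for all binary endpoints without an alternative. If denominators are about 100 or fewer and proportions about 95% or more, coverage of observed and NRI intervals falls well below 95%, and limits can exceed 100% or coincide. At 98% to 99% the shortfall can persist with several hundred patients (89.5% at n=400, p=0.98). For cohorts of 300 to 800 at 90% to 95% response, the effect is about 2 to 3 points of coverage and about half a point in the limits, which would change no reading of the results.

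All of this rests on assumed n and p. It concerns the reported precision of descriptive estimates only. It does not show that the trial's primary intervals are materially miscalibrated. Minor severity; a cheap improvement.

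**What to change.** In SAP 6.1.3, replace the Wald interval with the Wilson score interval for observed and NRI proportions.

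For MI and mNRI, use a Wilson-type interval built on the Rubin total variance. One form is the Wilson formula with n replaced by n/(1 + r), where r = (1 + 1/m)B/W, B is the between-imputation variance, W the mean within-imputation variance, and m = 100 as in SAP 6.3.2. Set r to 0 when every imputed dataset has 100% response. Do not pool on the logit scale, because the logit is undefined as soon as one imputed dataset has 100% response.

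The cost is a sentence or two in the SAP, a software option for the observed and NRI analyses, and a little programming for the pooled ones. Intervals become slightly asymmetric and sometimes wider. Where Wald already works, results barely change. Protocol 10.3.1 and SAP 6.1 require a protocol amendment only when a principal feature changes. This change should therefore need only a justification in the clinical study report.

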6.2. Adjustments for Covariates

The analysis on the primary outcome is descriptive. No adjustments for covariates will be needed.

6.3. Handling of Dropouts or Missing Data

Intercurrent events [ICH E9(R1)] are events which occur after the treatment initiation and preclude observation of a variable or affect how it should be interpreted. Examples of such events include treatment discontinuation due to death or adverse events (AEs), rescue treatment, and loss to follow-up. This section describes missing data imputation methods handling intercurrent events, commonly used in the long-term extension studies (Ratitch 2018), which will be implemented in this study.

6.3.1. As Observed Analysis

The “as observed” strategy is used in so-called “observed cases” or “completers” analysis ubiquitous in the literature but is not one of the recommended strategies in the ICH E9(R1). For this analysis, only data from completers at the visit are relevant, and therefore the analysis does not need to deal with missing data. This estimand is based on the subset of patients who would complete treatment through visit T if assigned to it. Therefore, this estimand is conditional and targets the effect of treatment conditional on completion of treatment through the time point of interest. Because the estimand is defined for a subpopulation conditional on an intercurrent

event, it is not causal. Summary based on observed data at each post-baseline visit will be provided.

6.3.2. Multiple Imputation

The multiple imputation (MI) can be used to implement the hypothetical strategy [ICH E9(R1)] for handling intercurrent events. This strategy is used to assess the effect of study treatment in a hypothetical trial where all patients have complete data and continue to take study treatment as directed without dropping out of the study or receiving rescue therapy. The MI method will be used to impute missing data with values mimicking what observations would have been had the patient not discontinued, but instead continued receiving their assigned treatment. The method assumes the data are missing at random, meaning missingness can be accounted for by collected variables. Missing outcomes for a discontinued patient are assumed to resemble those of a patient who remained in the trial and had similar baseline scores and outcomes during visits prior to the patient's discontinuation. The MI method will be the primary analysis method for longitudinal continuous outcomes and the secondary analysis for binary outcomes.

Non-monotone (that is, intermittent missingness) and monotone (that is, missingness due to treatment discontinuation) missing data will be imputed separately within each cohort under ITT population. Non-monotone missing data will be imputed using a Markov chain Monte Carlo method based on multivariate normal distribution for all outcomes. Monotone missing data will be imputed using a sequential predictive mean matching (PMM) method. The PMM method chooses a value randomly from a set of plausible observed values (e.g., in the case of sPGA, these are integers 0,1,2,3,4,5). The set consists of measured patient outcomes whose predicted values are close to the predicted value for the missing value from the simulated regression model (Heitjan and Little 1991; Schenker and Taylor 1996).

The steps of the MI method are as follows:

1. The intermittent/non-monotone missing data will be imputed with Markov chain Monte Carlo method with the imputation model based on multivariate normal distribution for the baseline and post-baseline scores. Values will be imputed until the dataset has a monotone missing pattern. Imputation will occur by calling SAS® PROC MI.
2. The monotone missing data will be imputed with the PMM method by calling SAS® PROC MI (with MONOTONE statement and option REGPMM). Imputation will occur sequentially beginning at visit 1 and proceed through visit T ($t=1, \dots, T$) utilizing previous outcomes for visits 1 to $t-1$ and baseline scores. Specifically:
 - a. First, predicted values for both observed and missing values are obtained from a regression model with coefficients sampled from the posterior predictive distribution of the parameters. The covariates of the model include the baseline score and previous outcomes of the variable of interest.
 - b. Following, a set is produced consisting of the k observations whose predicted values are closest to the predicted value for the missing observation at visit t . The missing value is then replaced by a value drawn randomly from this set. The value of k will be set at 5.
3. The above steps will be repeated for m times with different seed values to create m imputed complete data sets. The value of m will be set at 100.

4. For binary outcomes, imputation of the underlying continuous score will be completed first, as outlined in the above steps. The binary response will then be derived from the imputed complete data.
5. The final summary and inference will be conducted from the multiple datasets using Rubin's combining rules, as implemented in SAS® PROC MIANALYZE.

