6.3.4. Modified Non-responder Imputation

The modified non-responder imputation (mNRI) method will be used to implement the composite strategy [ICH E9(R1)] for handling intercurrent events. This strategy is used to assess the combination of the effect of study treatment with the occurrence of an intercurrent event. For the mNRI method, the patient's response status is defined based on if the patient meets the clinical requirements for response at the predefined time AND the treatment-related contraindication reasons of discontinuation. The outcomes after the discontinuation for treatment-related reasons are considered failure/nonresponse, as in nonresponder imputation (NRI). Discontinuation for reasons that are considered unrelated to study treatment will not be considered a contraindication, thus the resulting outcomes will be imputed by MI. Patients will be considered as non-responders for the mNRI analysis at the analysis time point if they do not meet the clinical response criteria or have missing clinical response data due to discontinuation from study treatment with a reason of adverse event (AE) including death, or lack of efficacy. For patients discontinuing treatment with any other reason, the MI method (Section 6.3.2) will be used. The mNRI method will be the primary analysis method for categorical efficacy and health outcome variables.

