6.9. Efficacy Analyses

[Table AMAH.6.3](#) includes the description and derivation of the efficacy/health outcomes measures and endpoints.

[Table AMAH.6.4](#) provides the detailed analyses including analysis type, method and imputation, population, and time point for efficacy/health outcomes analyses.

Table AMAH.6.3. Description and Derivation of Efficacy/Health Outcomes Measures and Endpoints

Measure	Description	Variable	Derivation/Comment	Definition of Missing/duplicate Components
sPGA	Static Physician Global Assessment (sPGA): the physician's global assessment of the patient's psoriasis lesions at a given time point. Plaques are assessed for induration, erythema, and scaling, and an overall rating of psoriasis severity is given using the anchors of: clear (0), minimal (1), mild (2), moderate (3), severe (4), or very severe (5).	sPGA score	Range from 0 to 5: clear (0), minimal (1), mild (2), moderate (3), severe (4), or very severe (5).	Single item, missing if missing. For the duplicate individual score at the same visit, choose the latest results.
		sPGA (0,1)	An sPGA assessed as either 0 or 1 with at least a 2-point improvement from baseline, which represents a clinically meaningful response of minimal plaque severity or complete resolution of plaque psoriasis.	Missing if sPGA is missing.
		sPGA (0)	An sPGA assessed as 0 with at least a 2-point improvement from baseline, which represents a clinically important endpoint indicating complete resolution of plaque psoriasis.	Missing if sPGA is missing.
PASI	Psoriasis Area and Severity Index (PASI): combines assessments of the extent of body-surface involvement in 4 anatomical regions (head and neck, trunk, arms, and legs) and the severity of scaling (S), redness (R), and plaque induration/infiltration (thickness, T) in each region, yielding an overall score of 0 for no psoriasis to 72 for the most severe disease (Fredriksson and Pettersson 1978).	PASI score	The composite PASI score is calculated by multiplying the sum of the individual-severity scores for each area by the weighted area-of-involvement score for that respective area, and then summing the 4 resulting quantities as follows: $\text{PASI} = 0.1(R_h + T_h + S_h)A_h + 0.2(R_u + T_u + S_u)A_u + 0.3(R_t + T_t + S_t)A_t + 0.4(R_l + T_l + S_l)A_l$ Where, R_h, R_u, R_t, R_l = redness score of plaques on the head, upper limb, trunk, and lower	If any individual score is missing, the PASI score will not be calculated, hence, missing.

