Measure	Description	Variable	Derivation/Comment	Definition of Missing/duplicate Components
	
Severity is rated for each index (R, S, T) on a 0-4 scale (0 for no involvement up to 4 for very severe involvement):
 
0 = none 1 = slight 2 = moderate 3 = severe 4 = very severe
 
The body is divided into 4 anatomical regions comprising the head (h), upper limb (u), trunk (t), and lower limb (l). In each of these areas, the fraction of total body surface area affected is graded on a 0-6 scale (0 for no involvement; up to 6 for 90% - 100% involvement):
 
0 = 0% (clear) 1 = >0% to <10% 2 = 10% to <30% 3 = 30% to <50% 4 = 50% to <70% 5 = 70% to <90% 6 = 90% to 100%
 
The various body regions are weighted to reflect their respective proportion of body surface area.
		
limb, scored 0-4 respectively;
 
T_h, T_u, T_t, T_l = thickness score of plaques on the head, upper limb, trunk, and lower limb, scored 0-4 respectively;
 
S_h, S_u, S_t, S_l = scaliness score of plaques on the head, upper limb, trunk, and lower limb, scored 0-4 respectively;
 
A_h, A_u, A_t, A_l = numerical value translation of % area of psoriatic involvement score for the head, upper limb, trunk, and lower limb, respectively.
 
PASI scores are treated as a continuous score, with 0.1 increments within these values.
	
		PASI change from baseline	Calculated as: observed PASI – baseline PASI.	Missing if baseline or observed value is missing.
		PASI percent improvement from baseline	
Calculated as:
 $\text{Percent improvement from baseline} = 100 \times \frac{\text{Baseline PASI} - \text{Observed PASI}}{\text{Baseline PASI}}$ 
If a patient has experienced an improvement, this measure will be positive. If a patient has experienced a worsening in the condition, this measure will be negative.
	Missing if baseline or observed value is missing.
PASI 75	A clinically meaningful response; ≥75% improvement in PASI score from baseline.	Missing if baseline or observed value is missing.		

Measure	Description	Variable	Derivation/Comment	Definition of Missing/duplicate Components
		PASI 90	Higher level of clearance; PASI 90 is a $\geq 90\%$ improvement in PASI score from baseline.	Missing if baseline or observed value is missing.
		PASI 100	Complete resolution of plaque psoriasis; a 100% improvement in PASI score from baseline.	Missing if baseline or observed value is missing.

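### SAP 6.3.2 fills intermittent gaps with unrounded normal draws, so multiple-imputation response rates are biased at gap visits, in a direction set by score prevalence and an unstated coding rule

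*SAP*

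**What the plan says.** SAP Section 6.3.2 splits missing data into two kinds. For intermittent gaps (step 1): "Non-monotone missing data will be imputed using a Markov chain Monte Carlo method based on multivariate normal distribution for all outcomes". Step 1 runs up to a defined point: "Values will be imputed until the dataset has a monotone missing pattern". Missing data after treatment discontinuation (step 2) are filled by predictive mean matching with k = 5, which returns values that occur on the scale; the SAP's own example is "in the case of sPGA, these are integers 0,1,2,3,4,5". Step 4 covers binary outcomes: "The binary response will then be derived from the imputed complete data". No minimum, maximum, rounding or rule for a negative or fractional draw is given.

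Table AMAH.6.3 defines the endpoints for scores as assessed. sPGA (0,1) is "An sPGA assessed as either 0 or 1 with at least a 2-point improvement from baseline". For PASI, "PASI scores are treated as a continuous score, with 0.1 increments within these values", and PASI 100 is a 100% improvement, that is, a score of 0. sPGA (0), PSS symptoms = 0, PSSI = 0, NAPSI = 0 and PPASI 100 also rest on a score of zero.

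Section 6.3.2 makes MI primary for continuous outcomes and "the secondary analysis for binary outcomes". Table AMAH.6.4 lists MI for every binary endpoint, beside observed, NRI and mNRI. In the primary mNRI method (Section 6.3.4), discontinuation for an adverse event or lack of efficacy counts as non-response. Otherwise: "For patients discontinuing treatment with any other reason, the MI method (Section 6.3.2) will be used".

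**The concern.** A normal draw has no mass at any single value. On a scale where many patients sit at zero, draws spread to both sides of it, and the share counted as responders depends on how a value such as 0.3 or -0.4 is coded. The SAP leaves that to the programmer. It also treats the same score in two ways: on the scale after dropout, off the scale at a skipped visit.

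PASI 100, PSS symptoms = 0 and DLQI (0,1) with a 5-point improvement are Table AMAH.4.1 secondary endpoints planned for the clinical study report. If their MI rates carry an error that differs in size and sign by endpoint, the PASI 90, PASI 100 and sPGA (0,1) curves from the same patients are not comparable with one another. Section 6.9.5 plans no sensitivity analysis that would reveal this.

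**Working it through.** **Plan's own figures.** The documents give no gap rate, response rate or score distribution, so there is nothing to reproduce. The effect was simulated under stated assumptions.

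**Formula.** Whole-cohort shift at a visit = g × (imputed rate − true rate among gaps), where g is the share of the cohort with a step 1 gap at that visit.

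**Simulation A.** Originating baseline plus 21 visits; patient effect (variance 0.6) plus AR(1) error (variance 0.4, correlation 0.5, 0.8 or 0.95); 25% dropout by week 208; 6% gaps at on-treatment visits 2 to 20; n = 600. Five sPGA shares at 0/1: 5/25, 20/30, 45/40, 60/28 and 70/20%. PASI and PSS were given the same zero shares, and DLQI the same 0 and 1 shares. There were 240 runs, with Monte Carlo SE about 0.4 to 0.8 points. All of these are assumptions. Results in percentage points, coding a responder as at or below the cut-off:

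| Endpoint | Error within gaps | Shift, g = 6% | Shift, g = 1-10% |
|---|---|---|---|
| sPGA (0,1) | -21 to -8 | -1.3 to -0.5 | -2.1 to -0.1 |
| sPGA (0) | -40 to -2 | -2.4 to -0.1 | -4.0 to 0.0 |
| PASI 100 | -35 to +11 | -2.1 to +0.7 | -3.5 to +1.1 |
| PSS symptoms = 0 | -36 to +10 | -2.1 to +0.6 | -3.6 to +1.0 |
| DLQI (0,1) | -33 to -10 | -2.0 to -0.6 | -3.3 to -0.1 |
| PASI 90 | -12 to +0.4 | -0.7 to 0.0 | -1.2 to 0.0 |

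PASI 100 by zero share: -35 to -17 at 45-70% clear, -6 to +1 at 20%, +4 to +11 at 5%.

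**Simulation B.** N = 40,000, baseline plus 8 correlated visits, different score shapes. For a PASI-like score, lower-correlation scenario, imputed share at zero under four coding rules:

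- Exactly 0: 0% at any true rate.
- At or below 0: true 10% → 22.8%; 30% → 29.0%; 60% → 35.6%; 80% → 40.6%.
- Rounded and clipped: 10% → 23.1%; 60% → 37.5%.
- Truncated at 0, then rounded: 60% → 2.9%. A lower bound alone makes matters worse.

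For PASI 100 at a true 60%, at-or-below coding gives 0.10 × (35.6 − 60) = -2.4 points at 10% gaps. Literal equality gives 0.10 × (0 − 60) = -6.0 points at 10% gaps and -1.2 at 2%. At a true 10%, at-or-below coding gives 0.10 × (22.8 − 10) = +1.3. For sPGA (0), 80.1% → 34.5% gives 0.10 × (-45.6) = -4.6, so the 4-point upper figure belongs to zero shares up to 70%.

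**PASI 90.** Simulation A shows -2.2 to +0.4 within gaps at 86-91% response, but -12 to -1 at 51%. B gives 73% → 60%. Further runs with other score shapes give 84% → 77% and 80% → 64%. The largest, -16 points, is 0.10 × 16 = 1.6 points cohort-wide at 10% gaps.

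**Rounding and clipping in A, within gaps.** sPGA (0,1) -4.2 to +0.5; sPGA (0) -11 to +2; DLQI (0,1) -21 to -2; PASI 100 -31 to +11; PSS = 0 -28 to +13.

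**Predictive mean matching at gaps (k = 5).** A: -2.3 to +2.4 points over all endpoints. B: within about 3.5 points, mostly 1 to 2.

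**Continuous scores.** Under step 1 as written, mean error at gaps averaged over correlations was about 0.05 score points or less for sPGA, PASI, PSS and DLQI.

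**Yardstick.** 95% CI half-width at 88% with an assumed n = 600: 1.96 × √(0.88 × 0.12 / 600) = 2.6 points.

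**The case against.** MI is secondary for binary endpoints, three other analyses stand beside it, the study tests no hypothesis, and at 6% gaps every shift simulated in A lies inside the 2.6-point half-width. That stands and limits the importance. It does not remove the point, because the error is systematic and does not shrink with sample size.

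Gaps may be few: SAP Section 6.1 keeps out-of-window assessments, and dosing takes place at the site through Visit 13. The gap share also falls as patients leave; 6% of on-treatment patients after 25% dropout is 0.06 × 0.75 = 4.5% of the cohort. A missed visit just before dropout is already monotone and goes to step 2. All of this stands, and it is why the size is given as a range.

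DLQI and PSS borrowed assumed shapes from sPGA and PASI, and PPASI 100 and PSSI = 0 were not simulated under their own definitions. The DLQI figures are for a score of 0 or 1; they are not claimed to include the 5-point reduction. On measured scores with baseline of at least 5, that condition matters only for baseline 5 with a score of 1 (5 − 1 = 4).

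A reader might infer that the primary mNRI rates are directly biased. The documents do not establish that. Section 6.3.4 assigns patients to non-response or MI by reason for discontinuation, and an on-treatment gap fits neither rule. Nor is mNRI wholly clear of the problem: patients sent to MI have later values predicted from previous outcomes, some of which are step 1 draws.

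**Conclusion.** The concern holds for MI response rates at visits with intermittent gaps. It is an error in the stated method, not only a missing detail: step 1 as written gives wrong rates under every coding rule tried, although rounding and clipping nearly repairs sPGA (0,1). The direction is not fixed. It depends on how common the score is and on the coding rule; upward bias needs at-or-below or round-and-clip coding and a low true rate.

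Under assumed gaps of 1% to 10%, zero shares up to about 70% and at-or-below coding, the whole-cohort shift is about 0 to 4 points. Literal equality reaches about 6 points for PASI 100 at 60% clear and 10% gaps. PASI 90 cannot be called safe merely because most patients respond; it was little affected only near 86-91% response in Simulation A.

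Two wider readings are not supported. The continuous MI means, where MI is primary, are essentially unbiased. NRI and as-observed results do not use step 1 at all. The primary mNRI analysis is affected directly only if on-treatment gaps are sent to MI, and otherwise only indirectly through step 2. This should be corrected, but it does not undermine the primary analysis as written.

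**What to change.** Replace step 1 of Section 6.3.2 with text such as: *Intermittent missing values will be imputed by fully conditional predictive mean matching (PROC MI, FCS statement with REGPMM, k = 5), with observed values at that visit as donors. Values after treatment discontinuation are then reset to missing and imputed in step 2.*

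For the scalp, nail and palmoplantar subsets, prespecify the predictors as baseline and the two visits on each side. In 576 runs at n = 80 and n = 150 (NAPSI = 0 and PASI 100), that restricted model had errors of -1.7 to +3.1 points within gaps, against -36 to +13 for step 1 as written, and no run failed. Subsets below 80 were not tested.

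State in Section 6.3.4 that on-treatment gaps in mNRI are imputed by this step.

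If the normal model is kept, the minimum is to state that draws are rounded and clipped to the scale. That nearly repairs sPGA (0,1) and helps sPGA (0), but leaves PASI 100 and PSS = 0 wrong.

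The cost is a few SAP sentences, a different PROC MI statement, and slightly more programming and run time. No new data are needed.
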